**The Effect of Using Dexamethasone Tablets Vaginally for Improving
Cervical Bishop Score in Nulliparous Pregnant Women: A Randomized Clinical Trial**

NCT number: NCT05070468

Date of the document: 01/09/2021

Scientific Background

Inducing labor can be required as a therapeutic option. This requires stimulating uterine contractions before the spontaneous onset of labor. The most common indications for labor induction may include gestational or chronic hypertension, severe fetal growth restriction, preeclampsia, eclampsia, gestational diabetes, and post-term pregnancy. Ending a pregnancy can be needed when there is premature rupture of membranes without labor, oligohydramnios, or concerns related to fetal statuses, such as non-reassuring heart sounds (1, 2). Two primary techniques are used for cervical ripening when the cervix is unfavorable to facilitate the ripening process. The techniques can be mechanical interventions and/or the application of pharmacologic agents. Techniques like the administration of prostaglandins (e.g., Misoprostol), extra amniotic saline infusion (EASI), traction on the cervix with a Foley balloon catheter, and/or hygroscopic cervical dilators are used (3, 4). In nulliparous pregnant women, the cervix has a smooth, round external os. The average time from induction to delivery is between 15 to 20 hours. The cervical ripening phase can take up to 12 hours before the start of labor. Labor may be prolonged by about 10 percent of pregnant women, which can cause maternal and/or fetal risks. These risks include antepartum and postpartum hemorrhage and maternal and/or neonatal infection, leading to maternal, fetal, or neonatal death (5). Therefore, labor induction is essential in managing prolonged labor (6, 7).

Corticotropin-releasing hormone (CRH) is a principal regulator of the hypothalamic-pituitary-adrenal axis. CRH is released from the placenta and fetal membranes during pregnancy. Plasma CRH levels observed during labor peak during vaginal delivery (serum levels ranging from 2 to 3000 pmol/liter during labor) (6, 8, 9). The CRH functions as the “surveillance and response” for the placental. This allows the fetus to detect threats to survival, and if viable, the fetus can adjust its developmental course. In 2007, O'Sullivan et al. reported that congenital adrenal hyperplasia in the fetus is associated with 21-hydroxylase deficiency. In addition, a late gestational rise may lead to impaired cortisol production by the fetal adrenal gland (10).

Studies by Mohaghegh et al. and Latif et al. demonstrated that glucocorticoids like dexamethasone play a pivotal role in cervical ripening and aid labor induction (2, 8). Prior studies have used dexamethasone as the chosen glucocorticoid to investigate its role in labor induction. The effect

of dexamethasone on the interval length at the beginning of labor induction has been explored, as its effects at the beginning of the active phase of labor. (3, 8, 11-14). However, there is a paucity of studies because of the high heterogeneity among pregnant women. There is a need for double-blind clinical trials to solidify the use of dexamethasone for improving cervical Bishop scores in pregnant women. As outlined, the role of corticosteroids in labor induction remains unclear. The effect of using corticosteroids vaginally for labor induction requires further investigations. Therefore, we undertook a triple-blinded randomized controlled trial (RCT) where dexamethasone was the chosen glucocorticoid used for labor induction. This study aimed to examine the effect of using dexamethasone administered vaginally and whether it can enhance the Bishop score and reduce the duration of the latent phase of labor in nulliparous pregnant women.

Methods

Study design

This was a triple-blinded randomized controlled trial conducted in Kamali Hospital, Karaj, Iran. Kamali Hospital is one of the teaching hospital subsets at Alborz University of Medical Sciences. Ethical approval was ceded to the ethical committee of Alborz university. The ethics committee approved the study protocol. The RCT was conducted between October 2019 and June 2021. It was registered as an RCT with the following ID number: IR. ABZUMS. REC1399.067. Additionally, it was registered on clinicaltrial.gov, NCT05070468.

A sufficient sample size is required to compare the mean of the two groups (15). Using a 95% confidence interval and power of 90%, it was estimated that at least 84 participants were required. The participants were randomly divided into two groups of 42 as either cases or controls. The statistician assigned the participants to two groups using a balanced block randomization method using allocation into quadruple blocks. There were six modes for each case, two participants were in the control group, and two were in the intervention group. Thus, the participants were selected using the table of random numbers and assigned the numbers one to six within the groups of four.

Objectives

The clinical trial investigators and researcher staff were involved in all aspects of the study design and administration of the RCT. This included screening pregnant patients to assess if they met the

study inclusion criteria. These criteria required being a nulliparous Iranian woman pregnant, having full-term gestation (≥ 38 weeks), with a singleton pregnancy, between 18 to 35 years of age, and having normal Body Mass Indices (BMI) of 18.5—24.9. Labor induction was started in the participants when the membranes ruptured without the initiation of labor. The fetus was required to be in cephalic presentation, as shown on an ultrasound; there was a Bishop score of ≤ 2 and an estimated fetal weight of 2500-4000 grams. Participants were expected to have had normal Non-Stress Test (NST) results. If the patient's obstetric physician indicated termination of pregnancy, they could be eligible and randomized into case and control groups by a statistician.

Exclusion criteria required the pregnant woman not to take any hormones or herbal medicines (traditional medicines), herbal/natural products, or conventional/prescribed medications during her pregnancy. Those who had the following pre-existing diseases, including diabetes mellitus, hypertension, a history of obstetric complications such as preeclampsia or eclampsia, or HELLP (Hemolysis, Elevated Liver enzymes, and Low Platelets) syndrome, were excluded. If the pregnant individual had previously presented with fetal immobility/decelerations or a history of maternal bleeding, they could not be enrolled in the clinical trial.

To enroll eligible patients, the investigator explained the study to potential participants and asked them to consider being in the study after considering all the presented information. Written consent was obtained from all recruited patients. Once enrolled, the patients, investigators, and research staff were blinded to which groups the participants were allocated. Dexamethasone and placebo tablets were labeled Tablets A and B and delivered by the hospital pharmacist. The research staff was blinded to which tablets were the study drug. The study design required that the tablets be administered vaginally by the obstetrician. Fourteen dexamethasone tablets (0.5 mg) were administered in group A, and 14 placebo tablets were given in the same manner to the participants in group B.

Data collection

Data was collected using several tools, including interviews, observations, and a vaginal examination. The research staff designed a 2-page questionnaire which was used, and this included demographic information, i.e., current age, education, job, gravidity, parity, past medical history,

and BMI. The first and second Bishop scores, the latent phase duration, and delivery and intervention type were also recorded for each participant. The collected information was initially collected on paper forms.

Clinical intervention phase

During the intervention phase, the modified Bishop score was assessed; this comprised a physical examination that evaluated the cervical length, consistency, dilation and position, and fetal head station. Per the study protocol, an obstetrician placed fourteen tablets (either Tablets A or B) within the vagina during labor. The fetal heart rate was closely monitored, and any changes in the Bishop score within 6 hours were recorded. During this time, an obstetric physician undertook the labor induction for the study participants.

There were three types of interventions used. The first was when the pregnant woman did not require to be induced. These individuals had effective and robust contractions during labor. Therefore, further induction of uterine contractions was not performed, and labor took its natural course. Second, labor was induced when the pregnant woman did not have strong enough or effective uterine contractions. In these situations, Oxytocin was administered to aid in the induction if the patient had a Bishop score of five or more. Third, during labor induction in those participants assigned to the cases group, Misoprostol was administered if they had a Bishop score of less than 5. Once proper cervix ripening had been achieved, this indicated the termination of Misoprostol's effects. Labor induction continued with oxytocin until uterine contractions were satisfactory and strong. At each stage, from initial enrollment into the study, the onset of labor symptoms, and until the end of the latent phase of labor (4 cm dilation), the research staff followed and evaluated the individual women every 30 minutes. To further increase the reliability of the examination results, the patient's cervical dilation was established by two separate examiners to verify the result of the vaginal examinations.

Statistical analysis

The statistical analysis collected data from reviewing the participant questionnaires. This was converted for analysis using the SPSS statistical software version 25.0 (IBM Corporation, Chicago, IL, USA). A chi-squared test was used to assess any statistical hypotheses. Qualitative variables

were reported as percentages and frequency. Through the evaluation of data, the findings were evaluated by using the Kolmogorov-Smirnov and Shapiro-Wilk tests. Additional parametric and nonparametric analyses were performed. The subsequent assessment used the Mann-Whitney or T-Test (depending on the case). A p-value of ($P \leq 0.05$) was considered statistically significant in this study.

1. References:

1. Tenore JL. Methods for cervical ripening and induction of labor. *American family physician*. 2003;67(10):2123-8.

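### The misoprostol step is written for one arm only and contradicts the stated blinding; two shared tablet codes also leave the blind fragile, so the triple-blind claim needs qualifying

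*Combined protocol and SAP*

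**What the plan says.** All references are to the combined protocol and SAP. The end of Scientific Background and the start of Study design both call the trial triple-blind, without saying there who the blinded parties are. The Objectives section names them: "Once enrolled, the patients, investigators, and research staff were blinded to which groups the participants were allocated".

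On the tablets, Objectives says "Dexamethasone and placebo tablets were labeled Tablets A and B and delivered by the hospital pharmacist" and then gives the meaning of the letters: "Fourteen dexamethasone tablets (0.5 mg) were administered in group A, and 14 placebo tablets were given in the same manner to the participants" of group B. It adds that "The research staff was blinded to which tablets were the study drug". On allocation, Study design says "The statistician assigned the participants to two groups using a balanced block randomization method", with blocks of four and two groups of 42 called cases and controls.

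The Clinical intervention phase section has an obstetrician place the fourteen tablets, of one letter or the other. It then lists three courses. The first (no induction) and the second (oxytocin at a score of five or more) are not tied to a group. The third is: "during labor induction in those participants assigned to the cases group, Misoprostol was administered if they had a Bishop score of less than 5". No course is given for a woman in the control group whose score is below 5. Research staff evaluate each woman every 30 minutes until 4 cm, and "cervical dilation was established by two separate examiners". Under Data collection, both Bishop scores, the latent-phase duration and the intervention type are recorded for each woman.

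**The concern.** Two features of the text bear on the same claim.

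The first is a contradiction. Whoever gives misoprostol to the cases group only must know who is a case. The staff who see the women every half hour and record the intervention would then see a treatment that marks the arm.

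The second is a weakness of method. With two codes shared by all women and a constant meaning, knowledge gained about one woman carries over to all the others whose letters are known. Kits numbered by woman do not have this property.

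At stake is the credibility of outcomes that an examiner judges: the Bishop score and the 4 cm end of the latent phase. The second dilation examiner improves reliability. It gives no protection against a bias that both examiners share, and it is stated for dilation only, not for the other components of the Bishop score.

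**Working it through.** **1. The two sections side by side.** Objectives: three parties do not know the group. Clinical intervention phase: misoprostol depends on the group and on a score below 5. Study design uses cases and controls as the names of the randomised arms, so the cases group most naturally means the dexamethasone arm. Both statements cannot be followed literally, unless the person giving misoprostol falls outside all three blinded parties. Even then, research staff record the intervention type and would see its use. The Bishop score is followed over 6 hours, and induction takes place in that time, so arm-specific use could precede the second Bishop score as well as the end of the latent phase.

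**2. Who is named as blinded.** Patients, investigators and research staff are named. The administering obstetrician and the analyst are not named as such, and a statistician made the assignments.

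**3. Reach of one code break.** The plan's own numbers are consistent: 84/4 = 21 blocks, and 21 × 2 = 42 per arm.
- Shared codes: one break shows what A and B mean, so up to 42 + 42 = 84 of 84 arms are open to a person who holds the letters.
- Individual numbers: 1 of 84 directly. Someone who also knew her block could guess each of her three block-mates to be in the opposite arm and be right 2/3 of the time, since two of the three are.

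Only later assessments can be biased. If the break comes at woman k, 85 − k women are still to be assessed: 84, 64, 43, 22 and 1 at k = 1, 21, 42, 63 and 84. The mean over k = 1 to 84 is 85 − 42.5 = 42.5.

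**4. How the two features combine.** If misoprostol did go to cases only, a single use in a woman whose letter is known would show that A is the active tablet. The documents give no rate of use. If an assumed share q of the 42 cases received it independently, the chance of at least one use is 1 − (1 − q)^42: 57% at q = 2%, 88% at 5% and 99% at 10%.

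**5. Illustration of the effect on the test.** This is conditional on a break, on letters visible to assessors, and on an assumed between-arm scoring shift b of 0.25 to 0.5 SD. The documents supply none of the three. With no true effect and m exposed women, bias = (m/84) × b. The t-test has 82 df and noncentrality bias × √(42/2) = bias × 4.583. At m = 42.5 and b = 0.25, bias = 0.126 SD and noncentrality = 0.580.

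| Exposed women | False-positive rate, b = 0.25 | False-positive rate, b = 0.5 |
|---|---|---|
| 1 | 5.0% | 5.0% |
| 22 | 6.0% | 9.1% |
| 42.5 | 8.8% | 20.9% |
| 64 | 13.9% | 40.7% |
| Average over a break equally likely at any woman | 10.2% | 25.5% |

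The last row exceeds the 42.5 row because early breaks raise the rate by more than late breaks lower it. For scale, 42 per arm detects 0.716 SD at 90% power (two-sided 5% t-test; the plan does not state the sidedness). The biases at 42.5 exposed, 0.126 and 0.253 SD, are 18% and 35% of that.

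**The case against.** The best defence has four parts.

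- **The documents describe a working blind.** A statistician allocated, a pharmacist delivered, three parties are named as blinded, and research staff did not know which letter was the drug. This stands. While the key is unknown, seeing a letter gives no better than a 50% guess at the treatment.
- **A reader might infer that the blind was broken, or that printing the key is itself a breach.** The documents support neither. No break is reported, and only the placing obstetrician is described as handling the lettered tablets; nothing says that the examiners saw them. The text reports in the past tense a trial that ended in June 2021, so giving the meaning of A and B there is ordinary reporting after the event.
- **The misoprostol sentence may be a drafting slip.** This is plausible: the other two courses are written for any woman, and the control group has no stated course below 5. If it is a slip, the unblinding argument from misoprostol falls away. The contradiction in the text remains until it is corrected. A reader might also infer that the arms did receive misoprostol differently; one sentence of uncertain wording does not establish that.
- **The false-positive rates rest on an unsourced shift.** This also stands. They show how a break would act and do not estimate what happened. The 8.8% and 20.9% figures are rates at the mean exposure and should not be read as averages.

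Triple-blind also has some basis, since three parties are named. What it cannot be taken to cover is the administering obstetrician or the analyst.

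**Conclusion.** The point holds in two parts. First, the Clinical intervention phase and Objectives sections contradict each other on whether treatment after allocation could depend on the arm. This is a matter of the text and needs no assumption, and no view is taken here on which clinical rule is right. Second, the shared two-letter code is fragile by design: one break reaches up to 84 of 84 women, limited to those whose letter is known, against 1 of 84 directly with individual numbers. That reach follows from the stated method. Any resulting bias in the outcomes needs a break, visible letters and a scoring shift, none of which is documented. The documents therefore do not support a conclusion that the blind failed or that the results are biased. They do support qualifying the triple-blind label. The change should be made; confidence is medium, because the misoprostol wording may be an error of drafting.

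**What to change.** 1. Reconcile the misoprostol text in Clinical intervention phase with the blinding statement in Objectives, by stating what was done in each group. If misoprostol was in fact given by arm, withdraw the triple-blind claim for outcomes assessed after it: the latent-phase duration, and the second Bishop score where misoprostol came first.
2. Otherwise, limit the label to the parties that Objectives names (patients, investigators, research staff), say that the administering obstetrician and the analyst are not named as blinded, and state that the shared code did not protect against a single code break.
3. For any repeat or extension, have the pharmacist dispense individually numbered, identical-looking kits in the randomised order with no shared letter, and keep the list away from treating and assessing staff. This cannot apply to the completed trial.

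Items 1 and 2 cost a few lines of text, with no patients or visits. Item 3 costs relabelling by the pharmacist, who already delivers the tablets, a new list, and a look-up for each emergency unblinding.

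### The misoprostol rule names only the cases arm and gives controls below 5 no rule, so as written a latent-phase difference cannot be attributed to dexamethasone alone

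*Combined protocol and SAP*

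**What the plan says.** The Study design section randomises 84 women, 42 per arm, to be cases or controls. It also calls the arms the intervention and control groups, so the cases are the dexamethasone arm. Entry criteria, under Objectives, include an unfavourable cervix: "there was a Bishop score of ≤ 2 and an estimated fetal weight of 2500-4000 grams".

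The Clinical intervention phase section introduces the induction pathways without limiting them to an arm: "There were three types of interventions used". The three pathways are:

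- No induction, for women with effective contractions. No Bishop threshold and no arm are named.
- Oxytocin, for women with weak contractions: "Oxytocin was administered to aid in the induction if the patient had a Bishop score of five or more". No arm is named.
- Misoprostol, followed by oxytocin once the cervix has ripened: "during labor induction in those participants assigned to the cases group, Misoprostol was administered if they had a Bishop score of less than 5". The cases arm is named.

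Women were followed "until the end of the latent phase of labor (4 cm dilation". Shortening the latent phase is one of the two aims given at the end of the Scientific Background. For the between-arm comparison, the Statistical analysis section says: "The subsequent assessment used the Mann-Whitney or T-Test (depending on the case". It refers to further parametric and nonparametric analyses but names no covariate adjustment. The text under Objectives says that patients, investigators and research staff were blinded. Data collection says that the intervention type was recorded for each participant.

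**The concern.** Misoprostol is a ripening agent by the document's own account in the Scientific Background. If it was available to one arm only, the latent-phase comparison is dexamethasone plus conditional misoprostol against placebo plus an unstated regimen. Randomisation protects the comparison of those two packages, but it does not isolate dexamethasone within them. The planned two-group tests cannot separate the components.

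If the sentence is a slip, the trial may be sound, but the document then describes a comparison that was not run. Either way, a reader cannot tell what the latent-phase result estimates. The population makes this matter: all women start below the threshold of 5, so the pathway with the arm-specific wording is open to any case who needs induction and has not ripened enough.

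**Working it through.** **Step 1. Who gets what, as written.**

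| Situation | Cases | Controls |
|---|---|---|
| Effective contractions, any Bishop score | No induction | No induction |
| Weak contractions, Bishop ≥5 | Oxytocin | Oxytocin |
| Weak contractions, Bishop <5 | Misoprostol, then oxytocin | No rule stated |

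The arms differ only in the last row, and there the control entry is missing.

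**Step 2. Consistency with blinding.** An obstetrician holding tablets labelled A or B, blind to group, cannot decide on misoprostol by whether the woman is a case. So either the rule applied to everyone and the sentence is wrong, or someone giving misoprostol knew the arm. No other sentence decides between these.

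**Step 3. The plan's own figure.** The Study design section gives 84 women at 95% confidence and 90% power, with no difference or SD, so 84 cannot be reproduced forwards. Solving backwards with a two-sided 0.05 test (sidedness is not stated) and 42 per arm:

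- Normal approximation: d = (1.960 + 1.282) × √(2/42) = 0.707 SD.
- t-test with 82 degrees of freedom: d = 0.716 SD.

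This serves only as a yardstick. The point does not depend on the sample size.

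**Step 4. Illustration of size.** None of these inputs is in the document. Assume that dexamethasone is inert and that the same share s of each arm needs induction and is below 5. Misoprostol shortens the latent phase by m = 0.5 or 1.0 SD in that share of cases. Controls in that share get a treatment k times as effective: k = 0 is no ripening, k = 1 is the same rule or an equally effective one.

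- Net shift = s × m × (1 − k).
- Arm variance = 1 + s(1 − s) × (effect in that arm)².
- d = net shift ÷ √(mean of the two arm variances).
- Noncentrality = d × √(42/2), with 82 degrees of freedom.

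Worked case, s = 0.5, m = 1.0, k = 0: the shift is 0.50 and the variances are 1.25 and 1.00. So d = 0.50/√1.125 = 0.471, the noncentrality is 0.471 × 4.583 = 2.16, and the chance of P≤0.05 is 57%.

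Chance of P≤0.05, for m = 0.5 to m = 1.0:

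| Share s | k = 0 | k = 0.5 | k = 1 |
|---|---|---|---|
| 0.25 | 9% to 19% | 6% to 8% | 5% |
| 0.50 | 20% to 57% | 9% to 18% | 5% |
| 0.75 | 39% to 90% | 13% to 36% | 5% |

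A simulation of the s = 0.50 row (20,000 runs) agreed: at k = 0 it gave 19.7% and 57.2% for the t-test, and 19.0% and 54.7% for Mann-Whitney.

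At the extreme (s = 0.75, m = 1.0, k = 0) the shift of 0.75 has to be put on the pooled scale before it is compared with the yardstick: 0.75/√1.09375 = 0.717 SD, about 100% of 0.716.

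**The case against.** The strongest reply is that the sentence is a slip. Staff were blinded, the pathways are introduced without an arm limit, and induction is described for participants in general: "During this time, an obstetric physician undertook the labor induction for the study participants". On that reading the trial compares dexamethasone with placebo on a common induction protocol, and nothing is confounded. This is plausible, and it is why the point is put conditionally. It does not remove the need to act: the only rule on the page is arm-specific, and the benign reading needs a rule that the document does not contain.

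It can also be said that co-treatment was recorded and that percentages and chi-squared tests are planned, so a table of intervention type fits the plan. That stands, and it makes the remedy cheap. But a table by arm is not specified, and it would not supply the missing rule.

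A reader might go further than the text allows in four ways.

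- *That a woman had to gain at least 3 points to avoid misoprostol.* The no-induction pathway has no Bishop threshold, so effective contractions were enough.
- *That ripening method and arm coincide below 5.* Women below 5 in both arms could share the no-induction pathway, and silence about controls is not proof that they were denied misoprostol.
- *That controls might have had a stronger method, reversing the bias.* The Scientific Background mentions alternatives ("traction on the cervix with a Foley balloon catheter, and/or hygroscopic cervical dilators are used"), but as general background. None is among the three pathways listed for this trial.
- *That the second Bishop score is affected as well.* Induction took place in the same 6-hour period, but the text does not say whether that score preceded misoprostol. The point does not rest on it.

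**Conclusion.** The concern holds in conditional form, and the sentence must be fixed. As written, cases who need induction and remain below 5 receive a ripening agent for which controls have no stated equivalent, before the end of the latent phase. A latent-phase difference therefore cannot be attributed to dexamethasone alone. The same sentence is incompatible with the stated blinding, so it is either a drafting error or evidence that blinding was broken.

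The document does not show that bias occurred. With the assumed inputs above, any bias runs from none (same rule in both arms, 5%) to large (no ripening in controls: 20% to 57% with half of each arm subject to the rule, up to 90% with three quarters). Those figures illustrate the range and are not estimates. The attribution argument stands without them. Confidence is medium, because the slip reading is credible and the text cannot exclude it.

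**What to change.** **If one rule was used in both arms,** replace the sentence with an arm-neutral rule applied blind to group: no induction if contractions are effective; otherwise misoprostol if the Bishop score is below 5, continuing with oxytocin once the cervix is ripe, and oxytocin if the score is 5 or more.

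**In either case,** report misoprostol and oxytocin use by arm from the recorded intervention type, counting misoprostol followed by oxytocin separately from oxytocin alone. Do not adjust the latent-phase comparison for misoprostol. It is given after randomisation and depends on the Bishop score, which dexamethasone is meant to change.

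**If misoprostol was in fact confined to cases,** say so, state what controls below 5 received, and correct the account of blinding. Limit the latent-phase conclusion to dexamethasone plus conditional misoprostol against placebo plus whatever induction controls received.

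The cost is one corrected sentence and one table from data already collected. The trial ran to June 2021, and no new patients or examinations are needed. The downside falls only in the last case, where the dexamethasone-alone claim for the latent phase is lost.

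### Does the latent-phase comparison need a written rule for women delivered before 4 cm dilation?

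*Combined protocol and SAP*

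**What the plan says.** All references are to the combined protocol and SAP.

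- **Aim (end of Scientific Background).** Besides improving the Bishop score, the trial asks whether vaginal dexamethasone can "reduce the duration of the latent phase of labor in nulliparous pregnant women".
- **End of the duration (Clinical intervention phase).** Women were followed "until the end of the latent phase of labor (4 cm dilation" and, during that time, "the research staff followed and evaluated the individual women every 30 minutes". The starting moment is not stated.
- **Data (Data collection).** "The first and second Bishop scores, the latent phase duration, and delivery and intervention type were also recorded for each participant".
- **Test (Statistical analysis).** After normality checks: "The subsequent assessment used the Mann-Whitney or T-Test (depending on the case". There is no rule for censoring, missing values or analysis population.
- **Size (Study design).** "it was estimated that at least 84 participants were required", and the participants were split 42 and 42. No difference, standard deviation, powered endpoint or loss allowance is stated.
- **Co-treatment (Clinical intervention phase).** "Oxytocin was administered to aid in the induction if the patient had a Bishop score of five or more"; and "in those participants assigned to the cases group, Misoprostol was administered if they had a Bishop score of less than 5".

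**The concern.** A duration that ends at 4 cm does not exist for a woman delivered before 4 cm. She can be left out, given her time to delivery, or ranked longest, and the three choices can give different answers. The women were nulliparous with a Bishop score of 2 or less at entry, and the fetal heart rate was monitored, so early delivery is possible. With 42 per arm, a few women can matter.

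If the slowest dexamethasone women drop out, the benefit is overstated and false positives rise. If the slowest controls drop out, the benefit is understated and power falls. Equal loss in the two arms cannot be read from the text either. The Misoprostol sentence names only the cases group, so a control with weak contractions and a score below 5 fits none of the three intervention types described.

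**Working it through.** **1. The plan's own figure.** The 84 cannot be derived forward, because no difference or SD is given. Solved backward for 42 per arm, two-sided 0.05 (sidedness assumed) and 90% power:

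d = (1.960 + 1.282) × √(2/42) = 3.242 × 0.2182 = 0.707 SD (0.716 with the t distribution).

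Using this value for latent-phase duration assumes that duration was the powered endpoint. The document does not say so.

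**2. Assumption.** Let k women in one arm be delivered before 4 cm. The documents give no k; the values below are illustrative (k = 4 is 4/42 = 9.5% of an arm).

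**3. No true effect.** Mann-Whitney, 42 per arm before losses, 10,000 simulated trials, percentage with p ≤ 0.05 (4.8% with no loss):

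| Who is affected, and handling | k=1 | k=2 | k=4 | k=6 |
|---|---|---|---|---|
| Slowest k of dexamethasone arm left out | 5.5 | 7.2 | 12.5 | 19.6 |
| Slowest k of control arm left out | 5.6 | 7.3 | 12.2 | 19.4 |
| Slowest k of each arm left out | 5.5 | 6.1 | 7.6 | 9.0 |
| Random k of dexamethasone arm left out | – | 4.9 | 5.1 | 4.9 |
| Random k of dexamethasone arm ranked longest | – | 5.6 | 9.9 | 17.2 |
| Slowest k of dexamethasone arm ranked longest | – | 4.6 | 4.2 | 3.8 |

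The first two rows are one quantity by symmetry. At k = 4 the simulation standard error is √(0.125 × 0.875/10,000) = 0.3 points, so 12.5 and 12.2 do not differ. Nearly all the excess favours the arm with the losses (12.1 of the 12.5 points). With equal losses in both arms, the excess has no direction.

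**4. Using each woman's own delivery time.** Assume durations with mean 3 SD, and delivery at 30 to 90% of the true duration (on average 60%, so 40% is cut off). For four women delivered for unrelated reasons, the arm mean shifts by 4/42 × 3 × 0.40 = 0.11 SD in favour of their arm. Simulated Mann-Whitney rejection is about 7%. Losses unrelated to progress are therefore harmless only if the women are left out.

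**5. True effect of 0.716 SD, k = 4, women left out.**

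| Missing | Mean difference (SD) | Power |
|---|---|---|
| Nobody | −0.71 | 88% |
| Slowest controls | −0.53 | 71% |
| Slowest dexamethasone women | −0.89 | 97% |
| Random, one arm | −0.71 | 86% |

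**6. Would a rule written in advance settle it?** Compare the rows at k = 4. Leaving women out is right for unrelated losses (5.1%) and wrong for the slowest (12.5%). Worst rank is the reverse (9.9% and 4.2%). The right handling depends on why each woman was delivered, and a general rule cannot know that beforehand.

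**7. Does the event arise?** Data collection states a duration for every participant, and Clinical intervention phase describes follow-up to 4 cm. No section mentions delivery before 4 cm. Taken literally, k = 0 and every excess above vanishes.

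**The case for a change.** The strongest reply is that a duration recorded for each participant describes a field on a form. It does not say what was written when 4 cm was never reached, and a time to delivery would fill the field equally well. Whether 4 cm was reached is not a listed item; it would have to be rebuilt from the half-hourly evaluations, if they were kept. No loss allowance is stated. All of that stands, although 84 is given as a minimum without inputs, so an allowance cannot be ruled out.

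It supports a request for information, not a different analysis. The large figures need the slowest women to be lost from one arm only, which is an extreme for which the documents give no evidence.

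Two neighbouring points also stand, but neither changes the test:

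- **Start of the clock.** It is not defined. Staff were blinded, so there is no sign that different conventions were used by arm, and naming the start in the report closes the point.
- **Misoprostol sentence.** It sits badly with the blinding described under Objectives and leaves some controls undescribed. It may be only loose wording. Those passages must be reconciled, and intervention type, which was recorded, can be shown by arm. The documents do not link it to delivery before 4 cm.

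**Conclusion.** No change to the plan. The missing rule is a detail that analysts fill sensibly when they write up the trial: give the number delivered before 4 cm by arm, the reasons, and how those women were entered. If the number is zero, one sentence settles it. If it is not, a sensitivity analysis labelled post hoc shows whether the conclusion depends on them. The planned t-test or Mann-Whitney remains the main result either way. The trial ran from October 2019 to June 2021 and is described in the past tense, so a rule added now would probably come after the data.

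Size: nil if every woman reached 4 cm. With four assumed early deliveries in one arm, no true effect and Mann-Whitney, rejection ranges from about 4% to 12.5%, depending on reason and handling. The power figures also assume normal durations and that duration was the powered endpoint. The judgement rests on the statement that duration was recorded for each participant and on the absence of any reported early delivery. A material and unequal count by arm would limit what can be concluded about the latent phase, but would not show that the planned test was the wrong choice.
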